11.2.2. Symptoms

11.2.2.1. Difficulty breathing

The subject will be considered positive for difficulty breathing when one or several of the following items is reported in interview during the examination visit:

- Wheezing reported in interview during the examination visit or Dica (fields [CLN_SIGN.SIGN_CAT]="Wheezing" and [CLN_SIGN.SYMP_REP]="Y")
- And/or Stridor reported in interview during the examination visit or Dica (fields [CLN_SIGN.SIGN_CAT]="Stridor" and [CLN_SIGN.SYMP_REP]="Y")
- And/or Tachypnea reported in interview during the examination visit or Dica (fields [CLN_SIGN.SIGN_CAT]="Tachypnea" and [CLN_SIGN.SYMP_REP]="Y")
- And/or Flaring the nostrils when breathing reported in interview during the examination visit or Dica (fields [CLN_SIGN.SIGN_CAT]="Flaring Nostrils" and [CLN_SIGN.SYMP_REP]="Y")
- And/or any chest indrawing reported in interview during the examination visit or Dica (fields [CLN_SIGN.SIGN_CAT]="Chest indrawing" and [CLN_SIGN.SYMP_REP]="Y")

Please note that the symptoms taken into account are the ones reported by the parents and that such symptoms could be present or not at the time of examination visit.

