4. CASE DEFINITIONS (AMENDED 15-DEC-2017)

4.1. Primary Study

DEFINITIONS FOR LRTI SURVEILLANCE:

During the surveillance for LRTI, a case is defined as;

A child suffering from a potential LRTI.

Potential LRTI:

Suspected involvement of the lower respiratory tract if a child with clinical signs of RTI, defined as either a runny nose, blocked nose or cough, is believed to have difficulties in breathing in the opinion of the investigator/study staff, based on the symptoms reported by the parent(s)/LAR(s) during the surveillance phone contacts. Difficulty in breathing as suspected by the investigator/study staff through reported symptoms will then be objectively confirmed by the investigator/study staff by means of pulse oximetry and RR at an examination visit. If at least one of these parameters is outside of the pre-defined normal range (Refer to Table 3), the case will be considered as an LRTI for the surveillance part of the study.

A subject is considered to have difficulty in breathing if he/she shows signs of:

- Wheezing or stridor
- Tachypnea
- Flaring (of nostrils)
- Chest indrawings
- Apnea

Table 3 Normal ranges for RR and Sa02

RR	Sa02
\leq 60/min for a child below 2 months of age	\geq 95%, independent of the age of the child
\leq 50/ min for a child aged 2 - 11 months	
\leq 40/min for a child aged 12 - 24 months	

RR= Respiratory Rate; SaO2= Blood Oxygen Saturation; min = minutes

During the surveillance for LRTI, any potential LRTI that is not found to meet the criteria for an LRTI may need a subsequent objective assessment by the investigator/study staff.

Note: The investigator/study staff will do an initial assessment of a case reported for the examination visit as either RTI or LRTI, only to determine further study activities. The final classification of all the cases reported as either, RTI, LRTI or severe LRTI will be done during statistical analyses as per the definitions given below.

CASE DEFINITIONS FOR DATA ANALYSIS:

LRTI case definition and severity scale

During the analysis of the study on the full dataset available for each case, all cases identified during the surveillance for LRTI will be definitively classified as either RTI, LRTI or severe LRTI according to the LRTI case definition and severity scale described in Table 4, and also according to the classification of WHO and the classification used by Nokes *et al* [Modjarrad, 2016; Nokes, 2004] (see below).

RTI	LRTI	severe LRTI

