11.2.1.4. LRTI

11.2.1.4.1. Any LRTI (WHO definition)

The subject will be defined as LRTI positive according to WHO definition when he is presenting:

- history of cough or difficulty breathing,
- and a measured oxygen saturation < 95% or an increase of respiratory rate.

200150 (EPI-RSV-005 BOD)

Statistical Analysis Plan Amendment 1 Final

For derivation purposes we are characterizing 2 groups of items:

- Component A which gathers items used to derive history of cough and difficulty breathing,
- Component B which gathers the oxygen saturation and respiratory rate.

Component A:

The subject will be considered positive for Component A when one or several of the following items are reported in interview during the examination visit:

- Cough reported in interview during the examination visit or Dica (fields [EXAM_VS.SYMP_CAT]="Cough" and [EXAM_VS.SYMP_REP]="Y")
- And/or difficulty breathing as defined in section 11.2.2.1

Please note that the 2 symptoms: blocked nose and runny nose are not considered here for the derivation, indeed even if in the table 1 note 1 the case definition mentioned "Based on history reported by parents/LARs and includes difficulty breathing associated with nasal obstruction". (in fact it relates to how the data is intended to be collected in future trials where the mother is asked does the child have difficulty breathing yes or no. It is meant to qualify that if the child's breathing difficulty is due to only blocked nose if the mother says its difficulty breathing it is. However, in this study we don't have the question difficulty breathing and so we cannot know whether the blocked nose was or not associated with difficulty breathing in the mothers view)

Component B:

The subject will be considered positive for Component B when one or both of the following statement is reached:

- Blood Oxygen Saturation <95% (field [CLN_SGN2.BLSAT_V])
- And/or Increased Respiratory rate as defined in section 11.2.2.2

Please note that Blood Oxygen Saturation and respiratory rate are measured during the examination visit.

The subject will be defined as LRTI positive according to WHO definition when he is positive for Component A AND positive for Component B.

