11.2.1.4.3. Any LRTI (GSK case definition)

The subject will be defined as LRTI positive according to GSK case definition when he is presenting:

• RTI as defined in section 11.2.1.1

AND at least one or both of the following:

- Blood Oxygen Saturation <95% (field [CLN_SGN2.BLSAT_V])
- And/or Increased Respiratory rate as defined in section 11.2.2.2

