11.2.1.4.4. Severe LRTI (GSK case definition)

Severe LRTI status according to GSK case definition will be defined positive when the subject is LRTI positive according to GSK case definition (see section 11.2.1.4.3) AND present at one of the following items:

- Blood Oxygen Saturation <92% (field [CLN_SGN2.BLSAT_V])
- **AND/OR** Irritability/agitation present at examination visit (fields [CLN_SIGN.SIGN_CAT]="Irritability" and [CLN_SIGN.SIGN_YN]="Y")
- **AND/OR** Lethargy/sleepiness present at examination visit (fields [CLN_SIGN.SIGN_CAT]="Lethargy" and [CLN_SIGN.SIGN_YN]="Y")
- **AND/OR** Any chest indrawing present at examination visit (fields [CLN_SIGN.SIGN_CAT]="Chest indrawing" and [CLN_SIGN.SIGN_YN]="Y")
- **AND/OR** Reduced/no vocalisation present at examination visit (fields [CLN SIGN.SIGN CAT]="No vocalisation" and [CLN SIGN.SIGN YN]="Y")
- **AND/OR** Apnoea > 20 sec present at examination visit (fields [CLN_SIGN.SIGN_CAT]="Apnoea" and [CLN_SIGN.SIGN_YN]="Y" and [CLN_SIGN.APNOEA20]="Y")
- **AND/OR** Cyanosis present at examination visit (fields [CLN_SIGN.SIGN_CAT]="Cyanosis" and [CLN_SIGN.SIGN_YN]="Y")
- **AND/OR** Stop feeding well present at examination visit (fields [CLN_SIGN.SIGN_CAT]="Stop feeding" and [CLN_SIGN.SIGN_YN]="Y").

Please note that the symptom used to define severity is the one measured by the medical team during the examination visit.

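### SAP 11.2.2.1 drops apnoea from difficulty breathing without declaring it, so a narrow group of hypoxaemic infants cannot meet the WHO or Kenyan comparator LRTI definitions

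*SAP*

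**What the plan says.** Protocol 4.1, under the definitions for LRTI surveillance, introduces its list with "A subject is considered to have difficulty in breathing if he/she shows signs of" and names wheezing or stridor, tachypnoea, flaring, chest indrawing and, last, apnoea. The WHO and Kenyan birth-cohort definitions for data analysis, later in the same section, use the term without listing signs.

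SAP 11.2.2.1 gives the derivation for analysis: "The subject will be considered positive for difficulty breathing when one or several of the following items is reported in interview during the examination visit". Its items are wheezing, stridor, tachypnoea, flaring and chest indrawing, in the protocol's order and without apnoea. Each item may come from the interview or the diary card. The section adds: "Please note that the symptoms taken into account are the ones reported by the parents".

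This list feeds Component A of the WHO definition (SAP 11.2.1.4.1), which needs cough or "difficulty breathing as defined in section 11.2.2.1". The Kenyan comparator (11.2.1.4.5) uses the same Component A. For WHO, nasal symptoms cannot substitute: "Please note that the 2 symptoms: blocked nose and runny nose are not considered here for the derivation". The sponsor's LRTI definition (11.2.1.4.3) does not call the list. It enters through "RTI as defined in section 11.2.1.1", meaning cough, runny nose or blocked nose.

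Apnoea is recorded. The sponsor's severity rule (11.2.1.4.4) uses "Apnoea > 20 sec present at examination visit", read from the same CLN_SIGN table that holds the five listed signs.

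**The concern.** The SAP list matches the protocol list up to its last entry and then stops, which looks like an oversight rather than a redefinition. SAP Section 9 sets out many changes from the planned analyses, but not this one. Protocol 9.10 requires changes to be described and justified in the final report.

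The affected definitions carry weight. WHO LRTI, WHO severe LRTI and the two WHO LRTI hospitalization endpoints are part of the co-primary incidence analysis (SAP 6.6.1). WHO is also the reference classification in the co-primary agreement analysis (SAP 6.8.1). An infant whose only reported breathing sign is apnoea can be severe on the sponsor's scale and a non-case on the reference, because of a missing line in a derivation rather than a real difference between the scales.

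**Working it through.** No stated figure in the plan bears on this point, so the check is of the rules themselves.

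**1. Worked case.** Take an RSV-positive infant with a runny nose, parent-reported apnoea and SaO2 88%. A clinical diagnosis is present and the respiratory rate is normal. There is no chest indrawing at examination, no cough, and none of the five listed signs is reported.

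| Definition | Entry criterion | Severity or oxygen criterion | Result under the SAP | With apnoea added |
|---|---|---|---|---|
| WHO LRTI | cough or 11.2.2.1: not met | below 95%: met | non-case | case |
| Kenyan comparator LRTI | same: not met | below 90% with diagnosis: met | non-case | case |
| Exploratory LRTI (SAP Table 4), if it uses the same list | not met | below 95%: met | non-case | case |
| Sponsor's LRTI | runny nose: met | below 95%: met | case | case |
| Sponsor's severe LRTI | sponsor's LRTI: met | below 92%: met | severe case | severe case |

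WHO severe LRTI (11.2.1.4.2) and the WHO LRTI hospitalization endpoints (11.2.1.9 and 11.2.1.10) all require WHO LRTI, so they fail too.

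**2. How wide the gap is.** Nine reported symptoms (cough, runny nose, blocked nose, the five listed signs, apnoea) give 2^9 = 512 yes/no patterns. With saturation 88%, a diagnosis present, normal respiratory rate and no indrawing at examination, every pattern was classified with the SAP list and again with apnoea added.

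- WHO: 4 patterns change from non-case to case.
- Kenyan comparator: the same 4. Exploratory: the same 4.
- Sponsor's LRTI: 0.

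The 4 are apnoea without cough and without any of the five signs, crossed with runny nose yes/no and blocked nose yes/no (2 × 2 = 4). Three have a nasal symptom and are sponsor cases but WHO non-cases. The fourth, apnoea with no RTI symptom, is currently a non-case on both. These are counts of patterns, not probabilities.

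**3. Direction in the agreement tables.** With WHO as reference and the sponsor's definition as the alternative (SAP Templates 20 to 23), each such episode is a false positive for the sponsor. It lowers specificity, PPV, overall agreement and kappa. With the sponsor's definition as reference and the Kenyan comparator as the alternative, it is a false negative for the comparator.

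**4. What is not affected.** RSV RTI with suspected lower-tract involvement (SAP 11.2.1.3 and 11.2.1.5) accepts any RSV-positive child who attended an examination visit, whatever the LRTI assessment. RSV hospitalization (11.2.1.8) needs only RSV positivity and inpatient care after that visit.

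**5. Illustrative size.** Protocol Table 13 gives 26 hospitalizations at 20 per 1000 in 1280 child-years. If 1% to 5% presented this way (assumption), 26 × 0.01 = 0.26 to 26 × 0.05 = 1.3 would fail the WHO-conditioned endpoint. Protocol 9.3 expects RSV LRTI at 8 times the hospitalization rate: 26 × 8 = 208. At 0.5% to 2% (assumption), 208 × 0.005 = 1.04 to 208 × 0.02 = 4.16 episodes would be missed. The exact interval in Table 13 for the 26 hospitalizations is 13.0 to 29.3 per 1000. Multiplied by 1.28 thousand child-years, that is 16.6 to 37.5 events, so the loss is well inside sampling error.

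**The case against.** The strongest reply is that the protocol's list is a surveillance definition. Protocol 4.1 says that staff assessment at that stage serves only to decide further study activities, and that final classification follows the analysis definitions. Those leave the term unlisted, and a footnote to SAP Table 4 bases it on history from parents. The SAP's surveillance questions (11.2.1.3) have no apnoea item either. On this view the SAP gave content to an open term and contradicted nothing. That stands in part: a reader might infer that the SAP overrides a protocol analysis definition, and the documents do not show that. But the surveillance list is the only content the protocol gives the term, and the SAP copies all of it but one entry. The SAP also treats apnoea as linked to difficulty breathing elsewhere: the footnote to Template 29 lists apnoea over 20 seconds among symptoms induced by it, as does protocol Table 4.

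Second, the gap is narrow. Cough and all five signs must go unreported at interview and in a diary that runs 14 days or longer, and SAP 11.2.1.11 pools symptoms across worsening visits. One report restores the case. This stands.

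Third, the sponsor's and WHO definitions already differ by design: a child with nasal symptoms only and SaO2 below 95% is discordant with or without apnoea. This also stands. Only the apnoea subset of that discordance comes from the omission.

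Fourth, the documents show apnoea only as an examination sign (SIGN_YN, APNOEA20). A parent-reported value (SYMP_REP) is likely, since the same table holds it for the other signs, but it is not shown. The fix must allow for that.

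**Conclusion.** The point holds as an undeclared mismatch between protocol 4.1 and SAP 11.2.2.1, with a definite but narrow consequence. It affects LRTI and severe LRTI on the WHO and Kenyan comparator definitions, and WHO LRTI hospitalization. The exploratory definition is affected if it uses the same list, which SAP Table 4 does not state. The resulting WHO-versus-sponsor discordance runs one way.

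Two stronger readings are not supported. A reader might infer that infants with apnoea drop out of the burden estimate or the hospitalization count. They do not, because the endpoint for the first co-primary objective and unconditioned RSV hospitalization still include them. A reader might also infer a material bias in incidence or agreement. The documents give no frequency for this presentation, and the shares used above are assumptions without a source. On those shares the loss is about one hospitalization or fewer and a handful of LRTI episodes, which would not change a conclusion. The case for acting rests on consistency, on the fact that the infants concerned are hypoxaemic, and on the low cost.

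**What to change.** Confirm whether CLN_SIGN holds a populated parent-reported value for apnoea. If so, add an item to SAP 11.2.2.1: apnoea reported at interview or in the diary, with CLN_SIGN.SIGN_CAT equal to Apnoea and CLN_SIGN.SYMP_REP equal to Y. If not, use the examination sign (SIGN_YN equal to Y) and say that this one item is observed rather than reported. State whether the 20-second qualifier applies; the list in protocol 4.1 carries none.

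Apply the change wherever 11.2.2.1 is called: Component A of the WHO and Kenyan comparator definitions, the exploratory definition if it shares the list (Table 4 should say so), and the start and end dates in 11.2.1.4.7 and 11.2.1.4.8.

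If the omission is deliberate, reconcile protocol 4.1 and SAP 11.2.2.1 by declaring and justifying it in SAP Section 9.

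The cost is a field check, one line of text and one line of programming, or a sentence in Section 9. No new data collection is needed if either field is populated.

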11.2.2.2. Increased respiratory rate

The subject will be considered to have increased respiratory rate if one of the following statement is reached:

- Respiratory rate (field [CLN_SGN2.RESPR_V])
- > 60/minute for subjects <2 months of age (fields [DEMOG.DOB_RAW] and [EXAM_VS2.ACTU_DT])
- > 50/minute for subjects 2-11 months of age(fields [DEMOG.DOB_RAW] and [EXAM_VS2.ACTU_DT])
- > 40/minute for subjects 12-24 months of age(fields [DEMOG.DOB_RAW] and [EXAM_VS2.ACTU_DT])

Please note that respiratory rate is measured during the examination visit.

11.2.3. Cord blood collection procedure

11.2.3.1. Duration between birth and cord blood collection

The duration between birth and cord blood collection expressed in hours will be computed using the birth date and time (fields [BIRTH_ST].[DOB_RAW] and [BIRTH_ST].[DOB_HH] and [BIRTH_ST].[DOB_MM]) and cord blood collection date and time (fields [LABSHEET].[SAMPRDAT] and [LABSHEET].[SAMP_HH] and [LABSHEET].[SAMP_MM]).

11.2.3.2. Duration between cord blood collection and centrifugation

The duration between cord blood collection and centrifugation expressed in hours will be computed using cord blood collection date and time (fields [LABSHEET].[SAMPRDAT] and [LABSHEET].[SAMP_HH] and [LABSHEET].[SAMP_MM]) and centrifugation date and time (fields [CORD_BL].[CENTR_DT] and [CORD_BL].[CENTR_HH] and [CORD_BL].[CENTR_MM]).

11.2.3.3. Duration between centrifugation and transfer of serum

The duration between cord blood collection and centrifugation expressed in hours will be computed using centrifugation date and time (fields [CORD_BL].[CENTR_DT] and [CORD_BL].[CENTR_HH] and [CORD_BL].[CENTR_MM]) and transfer of serum date and time (fields [CORD_BL].[SEPAR_DT] and [CORD_BL].[SEPAR_HH] and [CORD_BL].[SEPAR_MM]).

11.2.3.4. Duration between transfer of serum and storage

The duration between cord blood collection and centrifugation expressed in hours will be computed using birth date and time (fields [BIRTH_ST].[DOB_RAW] and [BIRTH_ST].[DOB_HH] and [BIRTH_ST].[DOB_MM]) and storage date and time (fields [CORD_BL].[TBFR_DT] and [CORD_BL].[TBFR_HH] and [CORD_BL].[TBFR_MM]).

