11.2.3.5. Duration of overall process

The duration between cord blood collection and centrifugation expressed in hours will be computed using and storage date and time (fields [CORD_BL].[TBFR_DT] and [CORD_BL].[TBFR_HH] and [CORD_BL].[TBFR_MM]).

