12.8. Practical implementation of protocol

12.8.1. Cord blood collection, storage, and processing

Template 56 Number and percentage of subjects according to the storage process of the cord blood sample, Overall and by country (PPS)

			Tot N=	al
Country	Characteristics	Categories	n	%
Overall	Cord storage condition until blood collection	Refrigerated		
		Wet ice		
		Room temperature		
		Processed immediately		
	Type of tube used to collect cord blood	Quest tube		
		Plain tube		
		Tube with gel separator		
		Other		
	Storage of the cord blood sample	Refrigerated		
		Wet ice		
		Room temperature		
		Processed immediately		
	Storage of the serum sample	Refrigerated		
		Wet ice		
		Room temperature		
		Processed immediately		
<each country=""></each>				

N = total number of subjects

n/% = number / percentage of subjects in a given category

Template 57 Duration between collections and completion of processing of cord blood sample (PPS)

		То	tal				
Country	Process duration	n	Mean	SD	Median	Minimum	Maximum
Overall	Duration of overall process (hours)						
	Duration of process between collection and centrifugation (hours)						
	Duration of process between centrifugation and transfer of serum (hours)						
	Duration of process between transfer of serum and storage (hours)						
Each country							

Overall process duration: Duration of process between collection and storage of cord blood sample

n= Number of subjects with cord blood sample in each country considered SD=Standard Deviation

200150 (EPI-RSV-005 BOD)

Statistical Analysis Plan Amendment 1 Final

Template 58 Descriptive statistics of [RSV-A - RSV-B] maternal antibody levels in cord blood according to [Storage condition until blood collection -Storage condition until centrifugation - Storage condition until tube was frozen] (PPS)

	[RSV N=	'-A –RSV	'-B] mater	nal a	ntib	odies		
Storage condition until blood collection	n	GMT	95% CI	SD	Q1	Median	Q3	Min/Max
Refrigerated								
Wet ice								
Room temperature								
Processed immediately								

N = total number of subjects

n= Number of events in each category

GM = Geometric mean SD=Standard Deviation

 $Q1 \text{ and } Q3 = 1^{st} \text{ and } 3^{rd} \text{ quantiles}$

Min/Max = Minimum/Maximum

Template 59 Descriptive statistics of [RSV-A - RSV-B] maternal antibody levels in cord blood according to tube type (PPS)

	[RSV N=	-A –RSV	'-B] mater	nal a	ntib	odies		
Storage condition until blood collection	n	GMT	95% CI	SD	Q1	Median	Q3	Min/Max

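### SAP 11.2.3.4 derives the serum transfer-to-storage time from birth instead of from serum transfer, so that one duration is overstated (minor; tertiary descriptive analysis only)

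*SAP*

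**What the plan says.** SAP 11.2.3 sets out five cord-blood durations, each from a pair of timestamps.

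- 11.2.3.1, birth to collection, starts from birth: "The duration between birth and cord blood collection expressed in hours will be computed using the birth date and time".
- 11.2.3.2, collection to centrifugation, starts from "cord blood collection date and time (fields [LABSHEET].[SAMPRDAT] and [LABSHEET].[SAMP_HH] and [LABSHEET].[SAMP_MM" (LABSHEET fields).
- 11.2.3.3, centrifugation to serum transfer, ends at "transfer of serum date and time (fields [CORD_BL].[SEPAR_DT] and [CORD_BL].[SEPAR_HH] and [CORD_BL].[SEPAR_MM" (CORD_BL fields).
- 11.2.3.4 is headed "Duration between transfer of serum and storage". Its rule says the duration "will be computed using birth date and time", naming the BIRTH_ST fields in full, and ends at the storage fields (CORD_BL.TBFR).
- 11.2.3.5, the overall process, "will be computed using and storage date and time". Nothing stands where the start point should be.

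The sentences that open 11.2.3.3, 11.2.3.4 and 11.2.3.5 all describe the collection-to-centrifugation interval, which is the subject of 11.2.3.2 only.

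The durations are used in SAP 6.11.1 and in the templates of SAP 12.8.1. Template 57 tabulates the overall, collection-to-centrifugation, centrifugation-to-transfer and transfer-to-storage times. Template 60 plots log10 antibody level against the same four. The Template 57 footnote defines the total: "Overall process duration: Duration of process between collection and storage of cord blood sample".

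**The concern.** The rule in 11.2.3.4 does not measure what its heading, its Template 57 row and its Template 60 axis all say it measures. Nothing else in the SAP corrects it. The birth fields are listed completely, so this is a stated wrong operand and not text lost in reading the file.

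At stake is how one part of the sample-handling objective is read. The transfer-to-storage plot is meant to show whether delay between separating the serum and storing it relates to the measured titre. With birth as the start, the horizontal axis becomes cumulative time since birth. Any relation between titre and the earlier steps, such as a long wait before centrifugation, would then appear in this plot and could be mistaken for an effect of the last step. Template 57 would also print a component longer than the total shown beside it whenever collection follows birth, if the total is programmed to its footnote.

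SAP section 9 drops the planned comparison of samples handled with and without the recommended procedure. The descriptive displays, including these, therefore carry what remains of the objective.

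**Working it through.** The documents state no figure for these durations, so there is nothing to reproduce. The check compares the operands of each rule with its heading.

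**Notation.** Let a = birth to collection, b = collection to centrifugation, c = centrifugation to serum transfer, d = serum transfer to storage.

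| SAP rule | Heading promises | Operands written | Result |
|---|---|---|---|
| 11.2.3.1 | a | collection and birth | a |
| 11.2.3.2 | b | centrifugation and collection | b |
| 11.2.3.3 | c | transfer and centrifugation | c |
| 11.2.3.4 | d | storage and birth | a + b + c + d |
| 11.2.3.5 | overall | storage and (blank) | undefined in this section |

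**Overstatement in 11.2.3.4.** Written minus intended = (a + b + c + d) − d = a + b + c, the time from birth to serum transfer.

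**Against the total.** The Template 57 footnote gives overall = b + c + d. The step as written exceeds it by (a + b + c + d) − (b + c + d) = a.

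**After correction.** 11.2.3.4 = TBFR − SEPAR = d, and 11.2.3.5 = TBFR − SAMP = b + c + d. The three steps then add to the total: 11.2.3.2 + 11.2.3.3 + 11.2.3.4 = b + c + d = 11.2.3.5.

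**Illustration with assumed times; none of these are in the documents.** Take a = 0.25 h, b = 2 h, c = 0.25 h, d = 0.5 h.

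- Rule as written: 0.25 + 2 + 0.25 + 0.5 = 3.0 h.
- Intended value: 0.5 h.
- Overall by the footnote: 2 + 0.25 + 0.5 = 2.75 h, which is 0.25 h shorter than the supposed component.

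Let b range from 0.5 h to 24 h with the rest fixed:

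- b = 0.5 h: 0.25 + 0.5 + 0.25 + 0.5 = 1.5 h.
- b = 24 h: 0.25 + 24 + 0.25 + 0.5 = 25 h.

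The written rule moves from 1.5 h to 25 h while the true transfer-to-storage time stays at 0.5 h. Under these assumptions, all of the spread on that axis would come from an earlier step.

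**Is the overall duration lost?** No. Its definition is in the Template 57 footnote, SAP 6.11.1 also speaks of the time from collection to the end of processing, the collection fields are in 11.2.3.2, and the storage fields are in 11.2.3.4 and 11.2.3.5.

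**Do other analyses use these durations?** The covariate lists for the Cox models (SAP 6.6.3, 6.9.1 and 11.1.5) contain no processing duration. The incidence analyses (6.6.1, 6.6.2) and the agreement analyses (6.8.1) do not use them either.

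**The case against.** The best defence is that a competent programmer would notice. The heading, the table row and the plot label all name transfer to storage, the SEPAR timestamp is given one rule earlier, and a step longer than its total would stand out in quality control. The repeated opening sentence marks the block as copied and imperfectly edited. This lowers the chance of wrong output but does not remove the error: the derivation annex is the specification a programmer works from, and on this rule it is explicit and wrong.

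A reader might go further and infer three things that the documents do not support.

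- *That the overall duration cannot be computed, so two of the four durations are wrong.* 11.2.3.5 is incomplete, but the footnote and 6.11.1 supply the start point. One duration is wrong as written, one is truncated but recoverable, and two have the right operands. It also cannot be excluded that the words missing from 11.2.3.5 were lost when the file was read.
- *That the whole handling objective would be answered with the wrong variable.* Templates 56, 58 and 59 cover storage conditions and tube type without using any duration, and two of the four plots in Template 60 rest on correctly specified steps.
- *That the antibody or incidence results are affected.* Protocol 6.5.5 says handling details are recorded partly so that the primary analyses can adjust for them, but the SAP's models contain no such term. SAP section 7 describes the analyses as descriptive, without hypothesis testing.

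**Conclusion.** The point stands in a narrow form. SAP 11.2.3.4 is wrong as written: it starts at birth when it should start at serum transfer, and so overstates that duration by a + b + c, the time from birth to serum transfer. The direction is certain if the timestamps follow the natural order. The size in hours cannot be given, because the documents contain no processing times. The certain reach is one row of Template 57 and one of the four plots in Template 60, within a tertiary, descriptive objective. The gap in 11.2.3.5 and the repeated lead-in sentences are drafting faults to tidy in the same edit. Severity is minor: an internal inconsistency in a derivation rule, with no bearing on any co-primary or secondary result in the SAP.

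**What to change.** Amend SAP 11.2.3 as follows.

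1. **11.2.3.4:** storage date and time (CORD_BL.TBFR_DT, TBFR_HH, TBFR_MM) minus serum transfer date and time (CORD_BL.SEPAR_DT, SEPAR_HH, SEPAR_MM). Remove the birth fields.
2. **11.2.3.5:** storage date and time (the same TBFR fields) minus cord-blood collection date and time (LABSHEET.SAMPRDAT, SAMP_HH, SAMP_MM), in line with the Template 57 footnote. The start should be stated outright, because the stray birth fields in 11.2.3.4 could be taken to belong here, and birth to storage would contradict the footnote.
3. **11.2.3.3 to 11.2.3.5:** replace the repeated opening words so that each names its own interval.

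A useful programming check is that the three steps from collection onwards add up to the overall duration for every sample with complete timestamps.

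The cost is a few lines of SAP text. Every field needed is already named in 11.2.3.2 to 11.2.3.5, so no new data are required. If Templates 57 and 60 have already been produced, the affected row and plot should be checked and rerun if they used the birth fields.
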